### **5.2.5 Duration / Study Day / Time**

Study day will be calculated as the number of days from first dose of study drug.

- date of event – date of first dose of study drug + 1, for events on or after first dose
- date of event – date of first dose of study drug, for events before first dose

### **5.2.6 Conventions for Missing and Partial Dates**

Missing and partial start and stop date will be imputed for analysis purposes as follows.

#### **Partial or missing stop date will be imputed as follows:**

- If the stop date is completely missing and the event has resolved, or the patient has stopped taking the concomitant medication, the stop date will be imputed as the date of the patient's last clinic visit in the study.
- If only the year is known, the stop date will be imputed as "31-Dec" of that year or as the date of the patient's last clinic visit in the study if in the same year.
- If the month and year are known, the stop date will be imputed as the last day of that month unless the stop date corresponds to the same month as the patient's last clinic visit in which case the date of patient's last clinic visit in the study will be used instead.

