#### **Missing start date will be imputed as follows:**

- If the stop date occurs on or after the start of study drug or the event / concomitant medication is ongoing, the start date will be imputed as the date of the first application of study drug.
- If the stop date occurs before the start of study drug, the start date of the event / concomitant medication will be imputed as the patient's screening date or the stop date of the event / concomitant medication whichever the earlier.

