#### **Partial start date (year present, but month and day missing)**

- If the stop date occurs on or after the start of study drug or the event / concomitant medication is ongoing, and the year is the same as the year of first dosing the start date will be imputed as the date of application of study drug. "If the year is different from the year of first dosing "01-Jan" will be used.
- If the stop date occurs before the start of study drug, the start date of the event / concomitant medication will be imputed as the "01-Jan" of the same year

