## **5.8 Prior and Concomitant Medications**

Prior medications are defined as all medications that were stopped in the 30 days before ICF sign-off, whereas concomitant medications are defined as medications taken on or after such date.

Separate tabulations will be produced for prior and concomitant medications presented by actual treatment group and overall for the Safety Analysis Set. Concomitant medications will be coded using the WHO dictionary (version B3 Global Mar-2023 or later) and summarized using Anatomic Therapeutic Chemical (ATC) Level 2.

Prior medication washout information will also be listed separately.

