#### ***5.11.5.5 Response rate, defined as a reduction of $\geq 20\%$ from Baseline in PANSS total score at Week 4***

As described in Table 2, prior to analysis the PANSS score data imputed under a MAR mechanism will be dichotomized as being a responder or non-responder, and then missing data due to discontinuation because of lack of efficacy or drug-related AE as well as any data collected after any relevant ICE (start of emergency or prohibited treatment prior to Week 4) will be imputed as non-responders. The resulting dataset will be analyzed using a logistic regression using the response status at Week 4 as a response and baseline PANSS score, and treatment as covariates, using the below sample SAS code:

```
ods output Diffs = <output-dataset>;
proc logistic data =  descending;
  by _imputation_;
  class trt01p (ref = 'Placebo');
  model response = trt01p baseline / link = logit;
  lsmeans trt01p / diff ilink om oddsratio;
run;
```

From the above, the log odds ratio alongside its standard error will be estimated and then pooled across imputed datasets to return one single estimate, which will be exponentiated (alongside its 95% CI) to obtain an OR for each treatment arm. The proportion of responders at day 28 will also

be descriptively summarized (based purely on observed data), with an approximate 95% CI reported, derived using the following sample SAS code:

```
ods output RiskDiffCol2 = <output-dataset>;
proc freq data = ;
  table trt01p*response / riskdiff (column = 2);
run;
```

This endpoint will also be analyzed by imputing all missing data as non-responders and fitting the same logistic regression as above, from which the OR for each arm will be estimated.

Response status will be listed in the general PANSS listing.

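### SAP 5.2.6 imputes stop dates without regard to what Screening recorded, so a drug that ended before consent can become concomitant and, for some partial start dates, be dated to Day 1

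*SAP*

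**What the plan says.** SAP 5.2.6 governs analysis and not just display: "Missing and partial start and stop date will be imputed for analysis purposes as follows".

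Stop dates:
- Month and year known: "If the month and year are known, the stop date will be imputed as the last day of that month". The exception is a stop in the month of the last clinic visit, "in which case the date of patient's last clinic visit in the study will be used instead".
- Year only: 31 December, or the last clinic visit if that falls in the same year.
- Wholly missing, drug stopped: the last clinic visit.

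Start dates, when the stop is on or after first dose:
- Missing: "the start date will be imputed as the date of the first application of study drug".
- Year only: if "the year is the same as the year of first dosing the start date will be imputed as the date of application of study drug"; for any other year, 1 January.
- Month and year: first dose if it is the dosing month, otherwise the first of the recorded month.

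SAP 5.8 splits medications at consent: prior ones stopped in the 30 days before it, while "concomitant medications are defined as medications taken on or after such date". For the PANSS response endpoint, SAP Table 2 names *taking* a prohibited medication before Week 4 as an intercurrent event under a composite strategy. SAP 5.11.5.5 says that "any data collected after any relevant ICE (start of emergency or prohibited treatment prior to Week 4) will be imputed as non-responders". Protocol 6.7 prohibits psychotropics outside a short permitted list. Neither document says which dates, recorded or imputed, identify an intercurrent event.

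**The concern.** The stop date is imputed first, and late. The start-date rules then use it as if it were observed. Nothing feeds in what the site already knows at Screening, namely that the drug had ended. One partial stop date can therefore move a pre-trial drug past consent, past first dose, and in some cases to a Day 1 start.

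Two outputs could be wrong. The prior and concomitant medication tables would place the drug on the wrong side of consent. If programmers identify intercurrent events from the imputed dates, a PANSS responder could also be scored a non-responder because of a drug that ended before the trial began. That error runs one way only: it lowers response rates and, if equal across arms, pulls the odds ratio toward 1.

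**Working it through.** The plan states no figure on this point, so there is none to reproduce. The check applies the rules literally and then counts.

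**Worked example (assumed dates).** An antipsychotic really stopped on 3 June 2024 and is recorded as June 2024. Consent is 5 June, first dose 12 June, last visit 23 July.

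- Imputed stop: 30 June, after consent and after first dose. SAP 5.8 now makes the drug concomitant.
- If the last visit were 21 June, the stop would be 21 June, still after first dose.

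| Start as recorded | Imputed start |
|---|---|
| Missing | 12 June (Day 1) |
| 2024 | 12 June (Day 1) |
| June 2024 | 12 June (Day 1) |
| March 2024 | 1 March |
| 1 March 2024 (complete) | 1 March |
| 2023 | 1 January 2023 |

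Only the first three rows create a *start* on Day 1 as 5.11.5.5 words it. In the last three the imputed stop alone could still count as *taking* the drug as Table 2 words it, so the two wordings can give different answers.

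**How often a month-only stop moves.** Assume a 30-day month, consent on day c = 1 to 30 with equal probability, and a true stop spread evenly over the L days before consent. A stop in the consent month is imputed to day 30, so it lands on or after consent. It is on or after first dose if c + screening length ≤ 30. The number of possible stops in the consent month is min(c − 1, L). The screening length of 7 days, extendable to 14, is from Protocol 7.1.

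- L = 30, on or after consent: sum of (c − 1) for c = 1 to 30 is 435; 435/900 = 48%.
- L = 30, on or after first dose, 7-day screening (c ≤ 23): 253/900 = 28%. With 14 days (c ≤ 16): 120/900 = 13%.
- L = 7, on or after consent: 21 + 23 × 7 = 182; 182/210 = 87%.
- L = 7, on or after first dose, 7-day screening: 21 + 16 × 7 = 133; 133/210 = 63%. With 14 days: 21 + 9 × 7 = 84; 84/210 = 40%.

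**Cross-check on the 2024 calendar.** If the drug stopped k days before first dose (k up to 28), a month-only stop moves to or past first dose on (366 − 12k)/366 of first-dose dates. With 7-day screening, a stop 1 day before consent (k = 8) gives 270/366 = 74%, 7 days (k = 14) 198/366 = 54%, 14 days (k = 21) 114/366 = 31%, and 21 days (k = 28) 30/366 = 8%. A stop 30 days before consent gives 0%.

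**Year-only stop.** If the stop year is the year of the last visit, the imputed stop is the last visit, so it always falls on or after first dose in a treated patient. For a stop 14 days before first dose, only first doses on 1 to 14 January escape: (366 − 14)/366 = 96% move.

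**Effect on the odds ratio (assumed rates).** With true response of 45% versus 30%, OR = (0.45/0.55)/(0.30/0.70) = 1.91. If 5% of responders in each arm are misclassified, the rates become 42.75% and 28.5% and the OR 1.87. At 1% it is 1.90.

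**The case against.** Several points on the other side stand, and they rule out stronger readings that a reader might infer.

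- *That the rules force non-response.* They do not. Neither document says that intercurrent events are derived from imputed dates. Protocol 10.4.1 has deviations, including receipt of prohibited treatment, assessed case by case before lock. Protocol 6.7 requires contact with the Medical Monitor within 24 hours when a patient needs medication, so a real Day 1 start would leave a trail. However, the SAP does not tie that review to intercurrent-event status, so imputed dates remain the default input.
- *That long-standing antipsychotics typically move to Day 1.* They do not. A year-only start in an earlier year becomes 1 January of that year, and an earlier-month start becomes the first of that month. For a drug begun before the dosing year, only a wholly missing start moves.
- *That Table 14.3.8 would show false on-treatment antipsychotic use.* The table counts use from consent onward. It already includes drugs tapered in Screening and standard antipsychotics started on Day 29, so an entry there does not signify on-treatment use. The error is a prior drug listed as concomitant.
- *That the percentages are shares of patients.* They are shares of records with a partial stop date, before the start-date condition and any review.

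Partial dates should also be uncommon where they matter most. Washout takes place in an inpatient unit, and exclusion 22 requires at least 5 half-lives before Baseline, which a month-only date often cannot verify. This is weaker for drugs that ended before admission, whose dates come from history.

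**Conclusion.** The point holds as a defect in a derivation rule, with limited reach. As written, SAP 5.2.6 can move a drug that ended before consent from prior to concomitant and, for three kinds of start date, to a Day 1 start. A false non-response follows only if the drug is a prohibited psychotropic and intercurrent events are taken from imputed dates, which the SAP leaves open.

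For medication records the effect is confined to the medication tables and the secondary response endpoint. The primary analysis is unaffected, because Table 1 handles these events by treatment policy and keeps the data. Pre-randomization records should be balanced across arms, so the expected result is slight attenuation: 1.91 to 1.87 even at an assumed 5% of responders. The frequency of partial dates is not in the documents; the number of patients is probably small. This is a minor, inexpensive correction.

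**What to change.** In SAP 5.2.6, before the start-date rules are applied:

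1. Cap an imputed stop date at the day before consent for a medication recorded at Screening as already stopped.
2. Cap it at the day before first dose for one recorded as ended during screening or washout.

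In the example the stop becomes 4 June. A missing start becomes the earlier of the screening date and the stop, also 4 June. The drug stays prior and no Day 1 start arises.

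In SAP Table 2 and 5.11.5.5, state that a prohibited- or emergency-treatment event resting on an imputed date counts only if confirmed in the deviation review of Protocol 10.4.1, done blinded and before lock. Requiring an observed start date alone would not do, because real prohibited use with a partial date would then be missed. Reconcile *taking* in Table 2 with *start of* in 5.11.5.5.

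Cost: a few SAP sentences, one programming check and one item in the review. Protocol 7.2.1 already has prior and current medications recorded at Screening, so no new data are needed, provided the eCRF (not available here) distinguishes stopped from continuing drugs.

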#### **Missing start date will be imputed as follows:**

- If the stop date occurs on or after the start of study drug or the event / concomitant medication is ongoing, the start date will be imputed as the date of the first application of study drug.
- If the stop date occurs before the start of study drug, the start date of the event / concomitant medication will be imputed as the patient's screening date or the stop date of the event / concomitant medication whichever the earlier.

#### **Partial start date (year present, but month and day missing)**

- If the stop date occurs on or after the start of study drug or the event / concomitant medication is ongoing, and the year is the same as the year of first dosing the start date will be imputed as the date of application of study drug. "If the year is different from the year of first dosing "01-Jan" will be used.
- If the stop date occurs before the start of study drug, the start date of the event / concomitant medication will be imputed as the "01-Jan" of the same year

### **Partial start date (month and year present, but day missing)**

- If the stop date occurs on or after the start of study drug or the event / concomitant medication is ongoing, the start date will be imputed as the first day of the same month and year unless this partial start date is in same month as the first application of study drug in which case the date of first application of study drug will be used.
- If the stop date occurs before the start of study drug, the start date will be imputed as the first day of the month and year of the partial start date.

All dates presented in the individual patient listings will be as recorded on the Electronic Case Report Form (eCRF).

### **5.2.7 Exposure to Study Drug**

Exposure to study drug will be calculated as follows:

$$\text{date of last dosing minus the first day of dosing} + 1$$

The exposure calculation will not take into account breaks in therapy. In addition to the above, The number of doses received will also be derived, to account for any break in therapy.

### **5.2.8 Treatment Compliance**

Treatment compliance will be derived as the ratio between the planned number of doses (i.e. 28 for patients completing the inpatient treatment period or the number of days from the first dose to the early termination date for patients not completing the inpatient treatment period, one for each planned day of the inpatient treatment period) and the actual number of doses received, as follows:

$$\% \text{ Compliance} = 100 \times \frac{\text{Actual Received Doses}}{\text{Total Planned Doses}}$$

Compliance will also be categorised as follows:

- <70% (poorly compliant)
- 70% to 90% (moderately compliant)
- 90% to 100% (fully compliant)

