4.1.1 Stopping Criteria

4.1.1.1 Individual Patient Stopping Criteria

Dosing of an individual patient will cease if any of the following criteria are met:

- SAE regardless of association to LB-102 or placebo according to the Principal Investigator (PI) and notification to the Medical Monitor.
- Any other event that is deemed by the Investigator or Sponsor to pose an unacceptable risk to the patient.

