7.2.14 Study Procedures for Early Termination and Withdrawal

If a patient is discontinued at any time after randomization into the study, the Investigator will make every effort to follow the patient and complete the follow-up procedures at an ET Visit as follows:

- Recording of concomitant medications (e.g., prescription and nonprescription medications)
- Full physical examination
- Bodyweight, BMI (derived programmatically from body weight and height measurements), and waist circumference
- Vital signs
- Resting 12-lead ECG (triplicate, further information in Section 8.2.3)
- Collection of blood and urine samples for clinical laboratory tests. Additional information is presented in the footnotes to the SoA (Table 7.1)
- Urine pregnancy test for all females of childbearing potential
- Assessment and recording of AEs
- PANSS
- CGI-S
- C-SSRS
- AIMS
- BARS

Confidential Page 64 of 102

- SAS
- Cogstate test

Confidential Page 65 of 102

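### SAP 5.2.8 counts an early leaver's planned doses up to the early-termination date, so a patient who took every due dose can be graded moderately or poorly compliant when that date falls after the last due dose.

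*SAP*

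**What the plan says.** SAP 5.2.8 gives percentage compliance as doses received over doses planned. (Its sentence states the ratio the other way round, planned to received; the displayed formula is the sensible one.) Planned doses are fixed for completers, "i.e. 28 for patients completing the inpatient treatment period", and for everyone else are "the number of days from the first dose to the early termination date for patients not completing the inpatient treatment period". Below 70% is graded poor, 70% to 90% moderate, and 90% to 100% full.

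Three other places bear on the denominator:

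- SAP 5.2.5: "Study day will be calculated as the number of days from first dose of study drug", and for dates on or after first dose it adds 1, so the end day is counted.
- SAP 5.2.7: length of exposure ends at the last dosing date, not at the ET date.
- SAP 5.9: the number of doses missed is tabulated, with no definition of its own.

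In the protocol, Section 4.1.1.1 says "Dosing of an individual patient will cease if any of the following criteria are met". After discontinuation, Section 7.2.14 asks the site to "complete the follow-up procedures at an ET Visit as follows". The list that follows contains no study drug administration.

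**The concern.** The denominator should count doses the patient was supposed to take. Tying it to a visit date adds any days between the end of dosing and that visit, and adds the visit day itself if no dose is given then. A patient who took every due dose is then reported as having missed some.

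It also sets two SAP derivations against each other. Take a patient dosed on Days 1 to 7 with ET on Day 8. That patient has 7 days of exposure under SAP 5.2.7, 7 doses received, and 8 planned doses under SAP 5.2.8. If the missed-dose count in SAP 5.9 uses the same planned number, it reports one missed dose that was never due.

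At stake is the accuracy of the compliance and missed-dose tables among patients who left early.

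**Working it through.** **Which day count applies.** For first dose on Day 1 and last dose on Day 28, the inclusive count gives 28 - 1 + 1 = 28, the SAP's own figure for completers. A plain date difference gives 27. The inclusive count also matches SAP 5.2.5, so it is used first.

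**Can the ET date follow the last due dose?** Yes.

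- The ET lists in Protocol 5.3 and 7.2.14 omit dosing.
- Footnote k of the Schedule of Assessments exempts the ET visit from the post-dose timing of SAS, BARS and AIMS.
- Protocol 4.1.1.1 and 4.1.1.2 stop dosing on stated criteria, and Protocol 9.2.3 stops drug at once in pregnancy and then calls for an ET visit.
- No maximum gap is given.

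**Formula.** Let a patient take all k due doses, one a day, with ET g days after the last dose.

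- Inclusive count: compliance = 100 × k / (k + g)
- Plain difference: compliance = 100 × k / (k + g - 1)

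**Result, inclusive count, ET by Day 28.** Cells show the number of doses taken, with none missed.

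| Gap g | Poor (<70%) | Moderate (70% to <90%) | Exactly 90% | Full (>90%) |
|---|---|---|---|---|
| 0 | none | none | none | 1-27 (all 100%) |
| 1 | 1-2 | 3-8 | 9 | 10-27 |
| 2 | 1-4 | 5-17 | 18 | 19-26 |
| 3 | 1-6 | 7-25 | none | none |

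Examples: 2/3 = 66.7% (poor); 7/8 = 87.5% (moderate); 14/15 = 93.3% (full); 25/28 = 89.3% (moderate, the best attainable with a 3-day gap).

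**Result, plain difference.** A 1-day gap gives 100% for all. A 2-day gap reproduces the cut-points of the g = 1 row. With no gap the score exceeds 100% (10 doses: 10/9 = 111%), which has no category, and one dose divides by zero.

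**Share affected, illustrative.** Assumptions: inclusive count, every ET visit one day after the last dose, and ET day d uniform on Days 2-27 (26 days). Compliance is then (d - 1)/d.

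- d = 2, 3: 50% and 66.7%, poor (2 days).
- d = 4 to 9: 75% to 88.9%, moderate (6 days).
- d = 10: exactly 90%, two categories (1 day).
- Graded below full: 8/26 = 31%, or 9/26 = 35% if the tie is counted.
- At the 25% dropout assumed in SAP Section 3: 0.25 × 31% = 7.7% and 0.25 × 35% = 8.7% of all patients.
- Mean understatement among dropouts: the average of 1/d over d = 2 to 27, which is 11 percentage points.

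If every ET visit falls on the last dosing day, all of these are 0.

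**After the fix.** Planned doses equal k, so compliance is k/k = 100% for any gap. The 7-dose patient moves from 87.5% to 100%, and the 2-dose patient from 66.7% to 100%.

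**The case against.** The best counter-argument is that the ET date may usually be the last dosing day. Protocol 7.2.10 says its Day 28 list also serves patients who discontinue earlier, and that list includes study drug administration. The Schedule of Assessments marks dosing in the column shared by Day 28 and ET. Protocol 5.3 asks for completion evaluations when dosing stops, where possible and reasonable. SAP 5.2.8 also adds that one dose is counted per planned treatment day, which could be read as excluding days after treatment ended. On the inclusive count, a dose on the ET day gives 100%.

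This stands as far as it goes. The protocol is mixed on dosing at the ET visit, and those passages need to be reconciled. A reader might infer that every fully adherent early leaver is capped at (d - 1)/d, or is always graded below full. The documents do not support that: it fails with no gap, and after 10 or more doses a 1-day gap still grades full. The objection does not remove the problem, because the ET date is undefined, the gap is unbounded, and the added phrase does not say where the count ends when treatment stops before the visit.

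The second counter-argument is that little depends on the result. SAP 5.10 makes compliance descriptive, SAP Section 8 drops the per-protocol set, and no efficacy analysis uses compliance. Exposure, doses received and a per-patient dosing listing (16.2.5.1) let a careful reader see what happened. This also stands, and it limits the importance of the point.

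**Conclusion.** The concern holds in conditional form. As written, the rule can grade a patient who took every due dose as moderately or poorly compliant whenever the ET date falls after the last due dose. On the inclusive count a 1-day gap is enough for anyone stopping after 8 or fewer doses. On a plain difference it takes a 2-day gap.

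The number affected cannot be fixed from the documents. It runs from 0% to about a third of dropouts, or about 8%-9% of all patients, under the assumptions of a uniform 1-day gap, exits spread evenly over Days 2-27 and 25% dropout. It is higher with longer gaps.

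A reader might go further and infer that true compliance among early leavers is near 100%, or that spurious low grades will cluster in particular arms. Neither is established. Dosing is supervised (Protocol 6.6), but Protocol 5.3 lists non-compliance with study drug as a reason for discontinuation, and the documents give no exit pattern by arm.

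The effect is confined to the descriptive compliance and missed-dose tables. This is a minor point, worth correcting because the written rule can produce a wrong reported number. The overlap at 90% taken alone would be clerical.

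**What to change.** In SAP 5.2.8, for patients who stop early, define planned doses as the scheduled doses from first dose through the last day a dose was due before treatment was discontinued. Take the end point from the treatment-stop date, not the ET visit date. Do not end the count at the last dose taken: doses refused just before stopping should still count as missed.

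Use the same planned count for the number of doses missed in SAP 5.9. Make the categories below 70%, 70% to below 90%, and 90% or more. Correct the sentence that states the ratio in the wrong order.

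The cost is about a sentence of SAP text and a small programming change. The downside is that the stop date must come from the dosing or disposition record instead of the visit date.
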